4.2 Rationale for sample size

Sample size is estimated for the 3 primary outcome measures: BADDS scores, DLPFC Glut levels, BOLD signal activation during the N-Back Task.

Assuming a type I, alpha, error of 5%, and 80% power, we anticipate being able to detect a 0.3 SD difference between within subject change under active LDX and placebo conditions with 88 participants. Based on our pilot data for total BADDS score, we will have 80% power to detect as small as an 8.4% difference in BADDS total score when comparing placebo to LDX administration. Given our pilot data from naturally menopausal women, this effect size corresponds to a 19% difference between active LSX and placebo in organization and activation for work, and 15% for attention/concentration BADDS subscales. We are conservatively powered for an effect size of 0.3 SD, meaning that we have sufficient power to examine a number of different covariates and possible predictors of outcome in this study.

Given our pilot data for levels of Glut in the left DLPFC, we will have 80% power to detect as small as a 2.6% reduction in Glut for active LDX administration compared to placebo. A similar 0.3 SD can be detected for BOLD signal in left DLPFC. This corresponds to a 25% difference in BOLD signal change between placebo and LDX for 3-back task.

5 Safety and Adverse Events

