2.1 General Design

To further our understanding of the mechanism of LDX treatment in women with executive function complaints after risk-reducing bilateral salpingo-oophorectomy (RRSO), participants will undergo multi-modal imaging (fMRI and 1H-MTS at 7 Tesla) pre- and post- a 6-week course of LDX (20-60mg/d) or placebo followed by an approximate 2-week washout before crossing over to the other condition. This study utilizes a double-blind, placebo-controlled, cross-over design. We will recruit 100 women who are between the ages of 35 and 58 years old. Subjects will be recruited from flyers posted around campus, paid advertisements, referrals from collaborators at FORCE (Facing Our Risk of Cancer Empowered), the Basser Center, and other medical settings where women who have undergone RRSO may seek treatment. Study subjects will be screened by a member of the research staff who can gauge whether the individuals are likely to meet study criteria. Potential participants who appear to meet criteria and express an interest in the study will have the option of completing the screening visit remotely or completing the visit in-office. Participants will also have the option to complete a remote version of the study.

In-Office Screening: Participants who report for an in-office screening will be presented with the full, written ICF where they will have the chance to review and sign it with the study CRC. After giving full, written informed consent, subjects will undergo screening for past and current psychiatric disorders with the Mini International Neuropsychiatric Interview (M.I.N.I) and complete several behavioral ratings and questionnaires concerning personal history. A urine sample will be collected from participants to do a urine drug screen. Subjects will then undergo a brief medical evaluation and electrocardiogram (EKG) conducted by the study PI ([name], M.D.) or key study personnel. Vital signs including blood pressure and pulse will be recorded. Women with a consistent systolic blood pressure of >145mm Hg or diastolic blood pressure >90 mm Hg after three readings at screening will not be enrolled and referred to their primary care doctors for further evaluation. Routine laboratory studies will include TSH, FSH and estrogen assays. If potential subjects have had these tests performed within the previous 6 months and can present their results, they will forgo additional blood work except that for genetics studies (4 mL)

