3.1 Target Population

We will recruit 100 women, aged 35 to 58 years old, who have undergone a RRSO within the previous 15 years and are currently reporting impairment in some aspect of their daily function. We anticipate a drop-out rate of 10%. Given that the composition of the proposed study population will reflect the Greater Philadelphia referral base, we will make attempts to enhance the recruitment of minorities, but we are limited by the racial and ethnic make-up of women who typically seek oophorectomy for prevention of breast and ovarian cancer.

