4.1 Statistical Analysis

Summaries of each outcome (BADDs scores, performance on the cognitive tasks, Glut, and BOLD signal) under each treatment condition (baseline, LDX, and placebo) will be examined using histograms, boxplots, and normal probability plots. Transformations of the outcomes will be considered as necessary to meet modeling assumptions. General linear regression (mixed models) will be employed to estimate the association between each outcome, treatment condition and cross-over sequence while accounting for the nonzero correlation among the repeated observations within individuals.

Aim 1: Total BADDs score at each time point will be examined for an interaction effect between time (pre vs. post) and treatment (LDX vs. placebo) to assess whether within-subject total BADDs score is significantly reduced post LDX treatment rather than post placebo. Baseline BADDs scores will be dichotomized at the median score and considered as a covariate in the mixed effects models. Additional interaction terms for baseline group by time (pre vs. post) and baseline group by treatment (LDX vs. placebo) will be added to the model to test whether treatment effects differentially affect those with higher baseline scores.

Aim 2: Similar models will evaluate BADDs subscores, cognitive task performance, and L-DLPFC Glut levels. Similar mixed models will assess associations between change in specific BADDs domains with identified deficits in executive function and change in DLPFC Glut levels.

Aim 3: We will quantify associations between baseline percentage BOLD signal change during performance of the n-back (3-back) and L-DLPFC Glut.

Current methods for fMRI analyses are as follows: Functional scans will be realigned, normalized, time-corrected, and spatially smoothed by an 8 mm FWHW Gaussian kernel. The time series will be high-pass filtered to correct for drift across the scan. For blocked designed experiments (3-back), regressors will represent trial conditions; for the event-related design

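### Section 4.2 infers adequate power for predictors of response from main-effect power; the planned median-split interaction has about 29% power at 0.3 SD and reaches 80% only near 0.60 SD

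*Combined protocol and SAP*

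**What the plan says.** Section 4.2 sets the error rates ("Assuming a type I, alpha, error of 5%, and 80% power") and says the trial can "detect a 0.3 SD difference between within subject change under active LDX and placebo conditions with 88 participants". It calls the 0.3 SD target conservative and draws a further conclusion: "meaning that we have sufficient power to examine a number of different covariates and possible predictors of outcome in this study". The section gives no power, detectable effect or sample size for any predictor or interaction.

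Section 4.1, Aim 1, plans one such analysis by name. Baseline BADDs is split at its median, and interaction terms for baseline group are added "to test whether treatment effects differentially affect those with higher baseline scores".

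On numbers, section 3.1 states "We will recruit 100 women, aged 35 to 58 years old" and expects 10% to drop out. On design, section 2.1 states "This study utilizes a double-blind, placebo-controlled, cross-over design".

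**The concern.** The 80% in section 4.2 belongs to the average LDX-placebo difference over all women. A predictor of response is a different quantity: the difference in that LDX effect between women with and without the predictor. With two equal halves, its standard error is twice that of the average effect, so power for the average says nothing favourable about power for the predictor.

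The sentence presents the second as a consequence of the first. If it stands, a null baseline-severity interaction could be reported as evidence that severity does not matter, backed by a power statement that the design does not meet for modifiers of the size the trial was built around.

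**Working it through.** **Inputs.** Alpha 5% and power 80% (section 4.2; sidedness is not stated). Effect 0.3 SD and 88 women analysed (section 4.2). 100 recruited and 10% drop-out, leaving 90 (section 3.1). Median split (section 4.1), so 44 v 44 of 88. I take the interaction by its stated purpose: does the LDX-minus-placebo difference in change differ between the two halves?

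**Scale.** Let SD be the standard deviation of the within-woman LDX-minus-placebo difference. This is an assumption; the next step shows that it reproduces the plan's figure.

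**1. The plan's own number.** For a paired comparison, n = ((z₀.₉₇₅ + z₀.₈₀)/0.3)² = ((1.960 + 0.842)/0.3)² = 87.2, rounded up to 88. The figure reproduces as two-sided; one-sided gives 68.7, so 69. At 88, power is 80.4% by the normal formula and 79.5% by the paired t. At 90 the paired t gives 80.4%.

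**2. Standard errors.**
- Average effect: SD × √(1/88) = 0.107 SD.
- Difference between halves: SD × √(1/44 + 1/44) = 0.213 SD, twice as large.

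**3. Power for a 0.3 SD difference between halves.** The standardised difference is 0.3/0.213 = 1.41, against a critical value of 1.96.

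| Women analysed | Normal | Two-sample t |
|---|---|---|
| 88 | 29.0% | 28.5% |
| 90 | 29.6% | 29.1% |
| 100 | 32.3% | 31.8% |

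**4. Difference detectable with 80% power at 44 v 44.** (1.960 + 0.842) × 0.213 = 0.597 SD; by the t distribution, 0.604 SD. Either way it is about 0.60 SD, twice the design effect.

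**5. The other reading of SD.** If 0.3 SD refers to a single change score, with correlation ρ between the two conditions, the standardised effect is 0.3/√(2(1 − ρ)). The documents do not give ρ, so this is a range of assumptions (t, 44 v 44):

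| ρ | Standardised effect | Interaction power |
|---|---|---|
| 0.3 | 0.254 | 22% |
| 0.5 | 0.300 | 29% |
| 0.7 | 0.387 | 44% |
| 0.8 | 0.474 | 59% |

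Power stays below 80% throughout. On this reading 88 is the 80%-power sample size only near ρ = 0.5, where the two readings coincide.

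**6. A continuous predictor.** By Fisher's z, the correlation detectable with 80% power at 88 is tanh((1.960 + 0.842)/√85) = tanh(0.304) = 0.295, or about 0.29. This is not interchangeable with 0.60 SD for a score cut at its median. Assuming bivariate normality, r = 0.29 puts the half means 2 × 0.29 × √(2/π) = 0.463 SD apart. The SD within each half is √(1 − (0.29 × 0.798)²) = 0.973, so the standardised difference is 0.463/0.973 = 0.476, or about 0.48, and power at 44 v 44 is about 60%.

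**The case against.** - **The plan sets no 0.3 SD target for a predictor.** This stands. The 29% is an illustration at the design effect, not a refutation of a stated figure. A modifier of about 0.60 SD between halves, or one continuous predictor with a correlation of about 0.29, would have 80% power. The defect is that adequacy is asserted with no target, on the strength of a calculation for something else.
- **The sentence also covers covariates.** This stands too. Adjusting for a baseline covariate costs little power. A reader might infer that adjusted analyses are underpowered; nothing in the documents supports that.
- **The 0.3 SD target is called conservative, and more than 88 women are planned.** A true average effect above 0.3 SD would raise power for the average, and the expected 90 women give 80.4% by the paired t. Neither rescues the interaction: a larger average effect does not make a difference between halves easier to find, and even all 100 women give only 32%.
- **Multiplicity.** A reader might go on to quote false-positive rates over five or ten predictors. The plan names one moderator, and those counts appear nowhere in it, so no such figure belongs here.
- **Importance.** The primary comparison is untouched, and sections 1.1 to 1.3 list no predictor analysis as an objective or outcome. That limits the consequence; it does not make the inference valid.

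**Conclusion.** The point holds for predictors of response. The 88 women reproduce as the smallest number giving 80% power for the average effect by the normal formula, and the claim of sufficient power for predictors does not follow from it. The planned median-split interaction has about 29% power for a 0.3 SD modifier and needs about 0.60 SD for 80%.

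This rests on two-sided 5% alpha, equal halves, and 0.3 SD measured on the within-woman LDX-minus-placebo difference. On the alternative scale the power ranges from 22% to 59% over the assumed correlations.

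A reader might infer that the sample size is wrong or that no predictor could be found. The documents support neither: the main calculation reproduces, and a sufficiently strong modifier is detectable. What is wrong is a stated property that the design lacks for modifiers of the design size.

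**What to change.** Replace the sentence in section 4.2 with:

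> With 88 women the study has 80% power to detect a difference in LDX effect of about 0.60 SD (of the within-woman LDX-minus-placebo difference) between two equal groups, such as the baseline BADDs median split. Smaller differences may be missed, and a null interaction will not be read as absence of moderation. Predictor analyses are exploratory.

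If baseline BADDs is analysed as a continuous score instead, state separately that the detectable correlation is about 0.29, and do not describe the two figures as equivalent.

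The cost is one sentence and a less favourable stated figure. No women, visits or analyses are added.

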5.1 Potential Risks

Risk of Vyvanse® (LDX): The reported adverse reactions to LDX treatment include: constipation, decreased appetite, diarrhea, dizziness, dry mouth, headache, increased sweating, mild irritability, nervousness, or restlessness, nausea, trouble sleeping, unpleasant taste, upper stomach pain, vomiting and weight loss.

The most common side effects reported by adults are decreased appetite, difficulty falling asleep, and dry mouth. LDX can cause an increase in blood pressure and heart rate, although it is not contraindicated in the treatment of individuals with stable hypertension (Huffman & Stern, 2004). While the likelihood that individuals will develop peripheral vasculopathy is very small, subjects will be monitored at each assessment for tingling and numbing sensations in their extremities. Sudden death has been reported in adults using stimulant medications within the normal dosing range. This type of serious event has not occurred with Vyvanse® but will be discussed with subjects as a potential adverse event of this class of medication. Although rare, the risk of serotonin syndrome increases when co-administered with other serotonergic agents (i.e., SSRIs, SNRIs, triptans). Women taking serotonergic medications will be briefed on potential symptoms and monitored at each visit for any side effects. Serious side effects will be minimized by short-term treatment, exclusion of women who would be at heightened risk for participation, and careful monitoring of the treatment.

Risk of ¹H-MRS operating at 7T: To date, no persistent adverse effects have been reported by facilities with magnetic field strengths at 7.0T. A metallic taste in the mouth, dizziness or nausea upon being moved into the magnetic field is not uncommon. This dizziness and nausea typically last less than 10 minutes and can be reduced by reducing the speed at which the subject is placed into the magnet. If experienced, the metallic taste usually goes away within minutes. In rare cases individuals may experience brief, intermittent sensations such as tingling in parts of their body during the scan. The FDA has authorized the use of the 7.0T magnets in humans. Some of the pulse sequences and/or RF coils are not FDA authorized but are considered non-significant risk investigational devices. All subjects will be informed of the possibility of having these sensations during the informed consent process. The 7.0T scanners are not approved in pregnant women and they are to be excluded from trials utilizing the 7.0T magnet. As the women in this study are not of child bearing potential, they will not be subjected to a urine pregnancy test before scans. All subjects will be screened for the presence of any metallic objects that they may be holding or have implanted in their bodies, and all potential subjects with metallic implants contraindicative to scanning at the 7.0T level will be excluded.

Experimental Device Clause: Some of the pulse sequences and/or RF coils are not FDA approved but are considered non-significant risk investigational devices.

Pregnancy Clause: Women in this study will be postmenopausal and are therefore unable to conceive.

Use of venipuncture for blood sampling: Inserting a needle into a vein is safe when done by professionals under clean conditions. Sometimes a bruise will occur at the puncture site and on rare occasions fainting, a blood clot, or an infection may form in the vein. If this occurs, appropriate treatment will be instituted immediately.

Clinical Assessments: Subjects will be administered a number of cognitive and behavioral assessments during the screening process and at follow-up visits. However, there is no risk associated with administering these assessments. Knowing the outcome of the assessments should

not make the subject feel any differently about themselves. We will not be sharing the results with anyone besides the subjects and the research team.

Genetics: In the laboratory, genetic samples will be labeled with a number only. Subject name or any other identifying information will not be attached to the samples in the research laboratory. This measure is taken to protect confidentiality, in addition to the following specific measures:

- a.) The genetic testing of all samples will be used for research purposes only. No results of genetic testing from this study will appear in any subject's medical record.
- b.) Genetic test results will not be made available to subjects, to their doctors, or to the other clinicians or any other clinical staff.
- c.) To protect confidentiality as much as possible, no computer records will be created that could be used to identify a subject's genetic or medical information individually. Thus, even if a "hacker" breaks into the laboratory computer system, there will be no information stored there that can identify any individual subject.
- d.) Information about genes will only be stored in [name] laboratory, using procedures described above to protect your confidentiality, unless the information has become completely stripped of information that could identify an individual subject.

In our experience at a previous academic institution, in which many hundreds of samples have been collected, no outside agency has ever tried to gain access to any research subject's genetics samples. [name] believes that the risk of this happening to any sample collected as part of this study is extremely small.

The goal of the genetic testing for the study is exploratory, not predictive.

5.2 Potential Study Benefits

There are no intended direct benefits for subjects in this study however participants may experience an improvement in their perceived cognitive functioning during the course of the study trials. Results from this clinical trial may help add to our understanding of treatment options for individuals experiencing executive function difficulties as a result of RRSO.

5.3 Risk/Benefit Assessment

This study represents more than minimal risk to the subject, as individuals will undergo neuroimaging and treatment with LDX, which they may never have otherwise taken. Should this study show that LDX administration improves executive function outcomes of interest and is correlated with changes in left DLPFC glut concentrations and BOLD signal, we will have additional evidence that psychostimulant –related changes in brain neurochemistry and neuronal function are clinically relevant.

5.4 Data Safety and Monitoring

The Principal Investigator (Dr. [name]) will be the primary source for data and subject safety monitoring. The research staff will meet weekly to discuss recruitment, retention, breaches of confidentiality, adverse events, and collected data. Subjects will be instructed to call study personnel as soon as possible in the event of side effects. If we have concerns about their physical and emotional health, we will share these concerns with the subjects' primary care physicians.

5.5 Resources Necessary for Human Research Protection

[name], the study Principal Investigator has had more than 20 years of experience conducting translational neuroscience research in human subjects focusing on the impact of sex hormones and neurosteroids on behavior and cognition in women. [name] is the recipient of 3 RO1 grants from the NIMH, NIDA, and NIA. She is also the recipient of several K awards from the NIH. [name] has extensive experience overseeing the conduct of research in her laboratory. She is personally responsible for all aspects of the study or delegation of duties to individuals she has trained over the years.

If an individual were to demonstrate the need for mental health services, they would first be referred to the Penn Center for Women's Behavioral Wellness (PCWBW) for evaluation by one of the Center's psychologists or psychiatrists. An appropriate treatment plan and/or referral would be developed as necessary. The PCWBW is housed in a large office building with 24-hour security. The Center's main offices at [name] are comprised of 8 clinical offices, one laboratory space, copy, fax and mail room, reception area and kitchen. In addition, there is both clinical and administrative space at Pennsylvania Hospital in the same area as Maternal Fetal Medicine outpatient services.

6 Data Handling and Record Keeping

6.1 Subject Confidentiality

This study will utilize directly-identifiable protected health information (PHI). PHI, as defined by HIPAA, means individually identifiable health information about an individual that is transmitted or maintained by electronic media or in any other form or medium. PHI includes demographic information that is created or received by a health care provider, health plan, employer, or health clearinghouse. PHI relates to the past, present, or future physical or mental health or condition of an individual; the provisions of health care to an individual; or the past, present, or future payment for the provision of health care to an individual; and identifies the individual or can reasonably be used as a basis to identify an individual. The following PHI will be collected for this study:

- Name
- Postal address information
- All elements of dates, such as birthdate and date of visit, (except year) for dates directly related to an individual and all ages over 89)
- Telephone and fax number
- Electronic mail addresses
- Social security numbers (*for study compensation*)
- Medical record numbers (*for ordering MRIs and medications*)

In accordance to University of Pennsylvania's policy regarding how PHI is handled, managed, and disseminated, study personnel will utilize an institutionally secured and managed network drive.

Institutionally secured and managed network drive: The PCWBW utilizes a departmental shared drive to securely store PHI. The PCWBW shared drive is managed and secured by The Penn Medicine Academic Computing Services (PMACS). Access to the shared drive requires password

access to a departmental device (PCWBW desktop or laptop) then additional password access to the departmental shared drive. After being granted access to the shared drive, one must have an encryption code to access the files storing PHI. Therefore, the only PCWBW employees that will have access to the PHI connected to this study will be the approved study personnel (Principal Investigator, Project Supervisor, Clinical Research Coordinators).

Any paperwork that includes PHI (such as SSN on subject compensation forms) will be kept in a locked draw within a locked office. To reduce the possibility of breaches in subject confidentiality, subjects will be given a unique identifier to place on their demographic information, questionnaires, behavioral ratings, and data from scan sessions. Only the study personnel will have access to the code. Five years after completion of the study, the subject code will be destroyed. Data will be destroyed 8 years after study completion.

